3.1 Mechanism Research Questions

Our mechanism research questions are:

Are the clinical effects of CBD mediated by the effects on the function of the medial temporal cortex and basal ganglia, and on glutamate levels in the medial temporal cortex and basal ganglia?

3.2 Mechanism endpoints

These outcomes will be based on measures made at visit 1, day 28, relative to those made at baseline:

Mechanism sub-study outcomes (measured at visit 1, day 28) :

1) Within-subject change in glutamate levels in the left hippocamus and caudate measured using ¹H-MRS.

2) Within-subject change in activation (indexed using the blood oxygen level dependent signal; BOLD) in the medial temporal cortex (MTL) and basal ganglia during a verbal memory task, and during an emotional (fear) processing task.

3) Within-subject change in resting state MTL and basal ganglia perfusion, as indexed using arterial spin labelling (ASL).

3.3 Trial Sub-Study Flowchart

Imaging and related activities only at London site

Outcome	Screening	0	1	2	3	4
Week No.	-1 to -3	1	4 (±3day)	13 (±7days)	26 (±14days)	30 (±7days)
MRI Study Exclusion criteria check MRI Scanning (fMRI,	X	X X	X			
1H-MRS, ASL) Pre-scanning Alcohol breathalyser		X	X			
Pre-scanning Nicotine smokerlyser		X	X			

4 Visit assessments

Baseline Visit (Randomisation, on Day 0) and Month One Visit (Visit window 1, at approximately day 28): Patients from the London hub who are participating in the Mechanism sub-study will take part in a neuroimaging session.

5 Outcomes

5.1 Mechanism sub-study outcome assessment

Neuroimaging data (¹H-MR spectroscopy, fMRI, and ASL) will be acquired using wellestablished protocols (below) on the 3T MRI scanner at the Centre for Neuroimaging sciences, King's College London. Each scanning session will last approximately 90 minutes.

5.1.1 Functional MRI (fMRI)

The BOLD signal will be acquired while participants perform a verbal memory task and an emotional processing task. Both paradigms have been used in previous fMRI studies of the effects of CBD ^{2,3} and the verbal memory task was also used in our proof-of-concept study.

1. Verbal memory task: In an encoding condition, subjects will be shown word pairs and asked to say ('yes' or 'no') if the words 'go together'. In a subsequent retrieval condition, they will be shown one from each pair and asked to say the word that it was previously paired with. Stimuli will be presented every 5secs in alternating blocks of 8 pairs and verbal responses will be recorded on-line.

2. Emotional (fear) processing task: Subjects will be presented with a series of 10 different facial identities, each expressing either a 50% (mildly fearful) or 100% (prototypically fearful) intensity of fear, or a neutral expression. They will be asked to indicate the gender of each face by pressing one of two buttons. Thirty different facial stimuli will be presented twice each for 2 seconds with the order of facial identities and expression type pseudo-randomized such that the same identity or facial expression type will not be presented successively.

5.1.2 Magnetic resonance spectroscopy (¹H-MRS)

Glutamate (Glu) levels in the hippocampus and caudate will be measured from a spectroscopic voxel placed over the left hippocampus and left caudate head, respectively (2cm³), using ¹H-MRS spectra (PRESS - Point RESolved Spectroscopy; TE = 30 ms; TR = 3000 ms; 96 averages) as previously employed at our centre ^{4,5}. We will employ the standard GE probe (proton brain examination) sequence, which uses a standardised chemically selective suppression (CHESS) water suppression routine. Although measuring Glu in these brain areas is technically difficult, a conventional PRESS acquisition following the techniques employed previously has provided good quality Glu signal ⁴ in CHR patients and allowed quantification of the major metabolites (Glu, Gln, NAA, Cho, Cr, ml). Shimming and water suppression will be optimised for each location, aiming for a line-width of less than 7Hz.

5.1.3 Arterial Spin labeling (ASL)

Resting cerebral blood flow (rCBF) will be measured using Continuous Arterial Spin labelling (CASL) scans acquired with a 3D Fast Spin Echo (FSE) spiral multi-shot readout, following a post-labelling delay of 1.5s using a sequence that we have employed before in this age group⁶. The spiral acquisition will use a short (4ms) TE, and 8 spiral-arms (interleaves) with 512 points in each arm.

5.1.4 Structural MRI

For image registration, both a high resolution T2-weighted Fast Spin Echo (FSE) image and high resolution T1-weighted Spoiled Gradient Recalled (SPGR) image will be acquired.

5.2. Mechanism sub-study Assessment of Efficacy

Mechanism sub-study outcomes (measured at visit 1, day 28): These outcomes will be based on measures made at visit 1, day 28, relative to those made at baseline.

Our mechanism sub-study parameters will be measured using the neuroimaging techniques: proton magnetic resonance spectroscopy (¹H-MR spectroscopy), functional magnetic resonance imaging (fMRI), and arterial spin labelling (ASL) (as described further in sections below), acquired using well-established protocols on the 3T MRI scanner at the Centre for Neuroimaging sciences, King's College London. The outcomes to be measured are:

1) Within-subject change in glutamate levels in the left hippocamus and caudate measured using ¹H-MRS.

2) Within-subject change in activation (indexed using the blood oxygen level dependent signal; BOLD) in the medial temporal cortex (MTL) and basal ganglia during a verbal memory task, and during an emotional (fear) processing task.

3) Within-subject change in resting state MTL and basal ganglia perfusion, as indexed using arterial spin labelling (ASL).

6 Sample size

6.1 Mechanism sub-study proposed sample size

One hundred CHR patients drawn from the main clinical trial; n=50 each from the CBD and placebo treatment arms.

6.2 Mechanism sub-study sample size justification

In our previous study ⁷ comparing hippocampal glutamate levels in CHR patients who make a transition to psychosis (Mean±SD: 7.81±1.01) compared to those who do not (Mean±SD: 7.06±1.23), the effect-size for the difference in hippocampal glutamate between the groups was 0.67 (estimated as standardized mean difference). Assuming that the effect of CBD treatment on hippocampal glutamate will be of a similar magnitude we estimated that to have 80% power to detect a difference between CBD and placebo on hippocampal glutamate at 28 days with an effect size of 0.67, using a two-sided t-test at p=0.05, we would require a sample size of n=37 per treatment arm. After inflating our sample assuming a 25% drop-out, we would need to recruit 100 participants for a minimum of 80% power.

In our proof-of concept study, we observed the within-subject change (day 1 minus day 21) in parahippocampal cortex activation (as estimated from the BOLD signal) in CHR patients during the verbal memory task between the CBD (Mean change \pm SD: 0.015 \pm 0.04) and the placebo (Mean change \pm SD: -0.042 \pm 0.05) treatment arms corresponded to an effect size of 1.25 (estimated as standardized mean difference). Assuming a similar effect-size in our proposed study, we estimated that to have 80% power to detect a difference between CBD and placebo on medial temporal cortex activation following 28 days treatment with an effect size of 1.25, using a two-sided t-test at p=0.05, we would require a sample size of n=11 per treatment arm.

In our proof-of concept study, we observed the within-subject change (day 1 minus day 21) in left putamen activation (as estimated from the BOLD signal) in CHR patients during the verbal memory task (encoding condition) between the CBD (Mean change \pm SD: -0.018 \pm 0.05) and the placebo (Mean change \pm SD: 0.043 \pm 0.06) treatment arms corresponded to an effect size of 1.10 (estimated as standardized mean difference). Assuming a similar effect-size in our proposed study, we estimated that to have 80% power to detect a difference between CBD and placebo on basal ganglia activation following 28 days treatment with an effect size of 1.1, using a two-sided t-test at p=0.05, we would require a sample size of n=14 per treatment arm.

7 Methods

7.1 Analysis of Clinical Efficacy Measures

For the mechanism (neuroimaging) sub-study outcomes (which focus on change from pre-treatment estimate to 28-day post-treatment estimate), only those with complete data for each of the mechanism outcomes will be analysed.

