All spectra will be analysed with LCModel version 6.3-0A ⁸ using a standard basis set of 16 metabolites (L-alanine, aspartate, creatine, phosphocreatine, GABA, glucose, glutamine, glutamate, glycerophosphocholine, glycine, myo-inositol, L-lactate, N-acetylaspartate, N-acetylaspartylglutamate, phosphocholine, and taurine), acquired with the same field strength (3 Tesla), localisation sequence (PRESS), and echo time (30 ms). Model metabolites and concentrations used in the basis set are fully detailed in the LCModel manual (http://s-provencher-.com/pages/lcmmanual.shtml). Poorly fitted metabolite peaks (Cramer-Rao minimum variance bounds of >20% as reported by LCModel) will be excluded from further analysis. Values of the water-scaled measure of

glutamate will be corrected for CSF content of the ROI using approaches employed before ⁹. We will examine whether the within-subject change in Glutamate level in the hippocampus and caudate (at 28 days relative to baseline) differs between the two treatment conditions by examining the interaction between time (baseline and 28 days) and treatment (CBD vs placebo) in a repeated measures ANCOVA.

References

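### The mechanism sub-study's complete-data rule, on its ordinary reading, lets failure of one imaging modality remove usable data from the others, and the glutamate comparison has almost no reserve to absorb that

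*Protocol*

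**What the plan says.** Section 7.1 of the mechanism sub-study appendix sets the analysis set: "only those with complete data for each of the mechanism outcomes will be analysed". The same sentence notes that the outcomes are changes from the pre-treatment estimate to the 28-day estimate.

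Appendix section 3.2 lists the outcomes: glutamate in the left hippocampus and caudate, BOLD activation in a verbal memory task and a fear-processing task, and resting perfusion by ASL. The sub-study flowchart (3.3) places scanning at baseline and at visit 1.

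Appendix section 6.2 sizes the sub-study on hippocampal glutamate. It seeks "80% power to detect a difference between CBD and placebo on hippocampal glutamate at 28 days". The inputs are a standardised difference of 0.67 and a two-sided 5% t-test, and the result is 37 per arm. It continues: "After inflating our sample assuming a 25% drop-out, we would need to recruit 100 participants for a minimum of 80% power". The two fMRI calculations in that section need only 11 and 14 per arm.

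Section 7.2 then gives each modality its own analysis. For spectroscopy it adds a quality rule: "Poorly fitted metabolite peaks (Cramer-Rao minimum variance bounds of >20% as reported by LCModel) will be excluded from further analysis".

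**The concern.** The restriction in section 7.1 falls on people, and its condition is complete data for each of the outcomes. Read in the ordinary way, a participant who fails on any one outcome is dropped from all of them. A failed caudate spectrum, an unusable fear-task run or a poor ASL acquisition at either visit would discard a valid hippocampal glutamate pair.

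Nothing planned in section 7.2 needs joint completeness, so the rule gives up data for no stated benefit. It also narrows the analysed group to those who got through every acquisition.

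Failures of single modalities are foreseeable from the protocol itself. Appendix section 5.1.2 acknowledges that glutamate is technically hard to measure in these regions, section 7.2.3 plans quality exclusions, and section 5.1 describes a session of about 90 minutes. The only allowance for loss is the 25%. What is at stake is the stated minimum power for the one outcome that determined the sub-study's size.

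**Working it through.** **Inputs from Appendix sections 6.1 and 6.2.** Glutamate "Mean±SD: 7.81±1.01" in those who made a transition and "Mean±SD: 7.06±1.23" in those who did not; effect size 0.67; two-sided 0.05; 80% power; 37 evaluable per arm; 25% drop-out; 50 per arm recruited.

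**Assumed inputs.** The protocol gives no failure rate for any modality, so the rates in step 4 are assumptions.

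**1. The plan's own figure.**
- Effect size: (7.81 − 7.06) / √[(1.01² + 1.23²)/2] = 0.75 / 1.125 = 0.666, stated as 0.67.
- Two-sample t-test, 80% power: 35.96 per arm at 0.67 and 36.33 at 0.666, so 36 or 37. The stated 37 is reproduced.
- Inflation: 37 / (1 − 0.25) = 49.3, so 50 per arm and 100 in total. The arithmetic is sound.

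**2. Reserve after the 25%.** 50 × 0.75 = 37.5 per arm. Power at 0.67 (two-sided t-test, noncentral t):

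| Per arm | Power |
|---|---|
| 37.5 | 81.7% |
| 37 | 81.1% |
| 36 | 80.05% |
| 35 | 78.9% |

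**3. Threshold.** Power is 80% at 35.96 per arm.
- Extra loss among those retained: 1 − 35.96/37.5 = 4.1%.
- Total loss: 1 − 35.96/50 = 28.1%.

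This is one or two participants per arm beyond the allowance.

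**4. Loss caused by the joint rule alone.** For hippocampal glutamate there are four other acquisitions: caudate spectroscopy, two fMRI tasks and ASL. Let f be the assumed share of attenders in whom a given acquisition is unusable at either visit, with failures independent and additional to the 25%. The number left per arm is 37.5 × (1 − f)⁴.

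| f | Left per arm | Power |
|---|---|---|
| 1% | 36.0 | 80.1% |
| 2% | 34.6 | 78.4% |
| 5% | 30.5 | 73.1% |
| 10% | 24.6 | 63.4% |

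**5. What the joint rule does not cause.** Failures of the hippocampal spectrum itself are lost under either rule. If 5% failed on top of the 25%, 37.5 × 0.95 = 35.6 per arm would remain, with 79.6% power, even under outcome-by-outcome analysis.

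**6. The fMRI comparisons sized in section 6.2.** At 25 per arm, power is 99.1% for an effect size of 1.25 and 96.8% for 1.1. These are not at risk.

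**The case against.** The strongest reply is that the sentence means complete cases outcome by outcome. Its own parenthesis ties completeness to the pre/post pair. Section 6.2 sizes the outcomes separately, section 7.2 analyses them separately, and the spectroscopy rule excludes peaks rather than participants. That reading is possible and fits the surrounding text, but the sentence does not say it, and an analyst applying it literally would drop people. The objection turns the point into a wording fault that may not reflect intent; it does not remove it.

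The second reply concerns the arithmetic. The 25% may already include unusable scans: section 6.2 does not say what it covers, and section 10.2 of the main protocol uses 32% for loss over a much longer follow-up. Failures within one session may also cluster, through movement or early termination. If the same participants fail everything, the joint rule costs nothing beyond glutamate's own losses. Both replies stand, so the figures in step 4 lie towards the pessimistic side for a given f.

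Third, these are secondary mechanism outcomes. The trial's primary and safety analyses are untouched. That limits the importance of the point, not its correctness.

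**Conclusion.** The point holds in conditional form. On its ordinary reading, section 7.1 discards usable data across modalities without need, and the glutamate comparison has almost no reserve beyond the 25%. If joint completeness is meant and failures elsewhere remove more than about 4% of retained participants, power falls below the stated 80%. Under independent failures on top of the 25%, a rate of 2% per acquisition is enough.

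A reader might infer that the rule by itself takes the glutamate comparison below 80%. The protocol does not support that. At exactly 25% total loss, power is 81.7%. A shortfall needs total loss above about 28%, and no failure rate is given from which to conclude that this will happen. Nor should glutamate's own failed spectra be counted against the joint rule, since they are lost either way.

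The conclusion rests on an effect size of 0.67, a two-sample t-test as in the plan's own calculation, and the assumed failure rates.

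**What to change.** Replace the sentence in Appendix section 7.1 with: *Each mechanism outcome is analysed in all randomised sub-study participants with usable baseline and day-28 data for that outcome; failure of one modality does not remove a participant from the others.* Report the denominator for each outcome by arm.

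In Appendix section 6.2, state whether the 25% covers failed scans and quality-control exclusions as well as drop-out. The replacement sentence removes losses caused by other modalities. It does not protect against hippocampal spectra failing beyond the 25%, so the scope of that allowance needs to be explicit.

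The cost is small: two sentences of text. The number analysed will differ between outcomes, so they will not all describe the same participants.

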7.2 Imaging data analysis

Imaging analysis will be overseen by the imaging expert [name]. In line with our hypotheses, for the purposes of our statistical analyses with the fMRI and ASL data, we will focus on two hypothesized regions of interest (ROI), based on previous literature and our pilot data. We will create two ROI masks: one for the 'medial temporal cortex' (which will include bilateral medial temporal cortices including hippocampi and parahippocampal gyri) and another for the 'basal ganglia' (which will include caudate, putamen and pallidum bilaterally) combined in separate study-specific masks.

7.2.1 fMRI analysis

fMRI data from the verbal memory and emotional (fear) processing tasks will be preprocessed using standard approaches and then analysed employing a non-parametric approach (XBAM version 4.1) that we have employed before in the analysis of data from these fMRI activation tasks^{2,3}. [name], one of the developers of the XBAM image analysis package and a co-investigator will advise on the analysis of imaging data. For each fMRI paradigm, we will examine whether the within-subject change in BOLD signal (at 28 days relative to baseline) within pre-specified ROIs differs between the two treatment conditions by examining the interaction between time (baseline and 28 days) and treatment (CBD vs placebo) in a repeated measures nonparametric analysis of co-variance (ANCOVA).

7.2.2 cASL analysis

rCBF images will be processed using FMRIB software library (FSL) software applications (www.fmrib.ox.ac.uk). Statistical analyses of rCBF data will be performed using the "randomise" program implemented within FSL, which uses a nonparametric permutation–based approach to infer statistical significance against a null data set generated by random permutation using approaches that we have employed before ⁶. We will examine whether the within-subject change in rCBF (at 28 days relative to baseline) within pre-specified ROIs differs between the two treatment conditions by examining the interaction between time (baseline and 28 days) and treatment (CBD vs placebo) in a repeated measures non-parametric ANCOVA.

7.2.3. ¹H-MRS quantification and analysis

All spectra will be analysed with LCModel version 6.3-0A ⁸ using a standard basis set of 16 metabolites (L-alanine, aspartate, creatine, phosphocreatine, GABA, glucose, glutamine, glutamate, glycerophosphocholine, glycine, myo-inositol, L-lactate, N-acetylaspartate, N-acetylaspartylglutamate, phosphocholine, and taurine), acquired with the same field strength (3 Tesla), localisation sequence (PRESS), and echo time (30 ms). Model metabolites and concentrations used in the basis set are fully detailed in the LCModel manual (http://s-provencher-.com/pages/lcmmanual.shtml). Poorly fitted metabolite peaks (Cramer-Rao minimum variance bounds of >20% as reported by LCModel) will be excluded from further analysis. Values of the water-scaled measure of

glutamate will be corrected for CSF content of the ROI using approaches employed before ⁹. We will examine whether the within-subject change in Glutamate level in the hippocampus and caudate (at 28 days relative to baseline) differs between the two treatment conditions by examining the interaction between time (baseline and 28 days) and treatment (CBD vs placebo) in a repeated measures ANCOVA.

References

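### Sub-study glutamate is sized on day-28 levels but tested as change, so the stated 80% power depends on an unstated baseline correlation; the planned tests also do not match the mediation objective

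*Protocol*

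**What the plan says.** Sizing (Protocol, Appendix section 6.2). The glutamate effect size comes from an earlier comparison of patients who "make a transition to psychosis (Mean±SD: 7.81±1.01) compared to those who do not (Mean±SD: 7.06±1.23". The text reports that "the effect-size for the difference in hippocampal glutamate between the groups was 0.67 (estimated as standardized mean difference". It carries this over to the treatment contrast "to have 80% power to detect a difference between CBD and placebo on hippocampal glutamate at 28 days with an effect size of 0.67", and "using a two-sided t-test at p=0.05, we would require a sample size of n=37 per treatment arm". Allowing for 25% drop-out, it arrives at 100 recruited, 50 per arm. The two fMRI calculations in the same section need only 11 and 14 per arm, so glutamate sets the sub-study's size.

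Analysis (Appendix sections 7.2.1 to 7.2.3). The endpoints are defined as within-subject change from baseline to day 28. Glutamate is tested "by examining the interaction between time (baseline and 28 days) and treatment (CBD vs placebo) in a repeated measures ANCOVA". ASL is tested through the "interaction between time (baseline and 28 days) and treatment (CBD vs placebo) in a repeated measures non-parametric ANCOVA", and fMRI in the same way. No covariate is named in any of the three, and no correlation between visits is given.

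Objective (Appendix synopsis and section 3.1). The research question is: "Are the clinical effects of CBD mediated by the effects on the function of the medial temporal cortex and basal ganglia", and likewise by glutamate levels in those regions.

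**The concern.** There are two separate mismatches.

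First, the 0.67 is a difference in glutamate levels divided by a between-patient SD of levels, and 37 per arm is the number for comparing levels at one visit. The planned test compares change. The SD of change equals the SD of levels only when r is 0.5. Below that, change is noisier than the sizing assumed; above it, less noisy. The protocol thus promises at least 80% power for a test whose power it has not calculated.

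Second, the sub-study asks about mediation, but the tests written down contain no clinical outcome. An effect of CBD on glutamate or brain activation is one link in a mediation argument and cannot establish the whole of it. Run as written, the sub-study could report what CBD does to the imaging measures but could not answer its own question.

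**Working it through.** **Inputs.** Group means and SDs 7.81±1.01 and 7.06±1.23; effect size 0.67; two-sided 0.05; 80% power; 37 per arm analysed; 50 per arm recruited; 25% drop-out (all Appendix sections 6.1 and 6.2). The correlation r between baseline and day-28 glutamate is not in the document, so r from 0 to 0.8 is taken as an assumed range. Equal SDs at both visits and no expected baseline difference between arms are also assumed.

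**1. The plan's own figure.** Pooled SD = √((1.01² + 1.23²)/2) = 1.125. Standardised difference = (7.81 − 7.06)/1.125 = 0.666, given as 0.67. The noncentral t gives 36 per arm for 0.67 and 37 for the unrounded 0.666. Power at 37 per arm is 81%. Then 37/0.75 = 49.3, rounded up to 50 per arm and 100 in total. The stated figures reproduce for a single-visit t-test on levels.

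**2. Power of the test that is planned.** With two visits, the time-by-treatment interaction is the between-arm difference in mean change. SD of change = SD × √(2(1 − r)), so the effect size becomes 0.67/√(2(1 − r)). At r=0.3 this is 0.67/1.183 = 0.566; at r=0.5 it is 0.67/1.000 = 0.67; at r=0.7 it is 0.67/0.775 = 0.865.

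**3. Baseline-adjusted alternative.** Residual SD = SD × √(1 − r²), so the effect size becomes 0.67/√(1 − r²), never below 0.67.

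| r | Interaction, 37 per arm | Baseline-adjusted, 37 per arm |
|---|---|---|
| 0 | 52% | 81% |
| 0.3 | 67% | 85% |
| 0.5 | 81% | 91% |
| 0.6 | 89% | 94% |
| 0.7 | 96% | 98% |
| 0.8 | 99% | over 99% |

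Simulation of the change-score test (20,000 runs each) gave 67.1% at r=0.3, 80.8% at 0.5 and 95.7% at 0.7. Simulation of the baseline-adjusted regression with its slope estimated (100,000 runs each) gave 80.5% at r=0, 84.2% at 0.3 and 90.3% at 0.5. Estimating the slope therefore costs under one percentage point, and power stays above 80%.

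**4. Correlation at which the interaction reaches 80%.** With 37 analysed per arm, r = 0.485; with 45, 0.37; with 50, 0.30.

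**5. Scope.** The fMRI effect sizes are built from SDs of change: parahippocampal (0.015 + 0.042)/√((0.04² + 0.05²)/2) = 1.26, stated as 1.25; putamen (0.018 + 0.043)/√((0.05² + 0.06²)/2) = 1.10. They are already on the scale of the interaction test, and at 37 per arm both exceed 99% power. ASL has no stated power.

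**6. Objective against tests.** The outcome variables in Appendix sections 7.2.1 to 7.2.3 are the BOLD signal, cerebral blood flow and glutamate, each compared between arms over time. CAARMS or another clinical measure appears in none of them. Section 6.2 powers only the step from treatment to imaging measure.

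**The case against.** The strongest reply is that the analysis fits the endpoint. The outcomes are defined as within-subject change, the interaction tests exactly that, and under randomisation a change analysis is valid and unbiased. This stands: the choice affects precision, not validity.

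A reader might infer that the sub-study is underpowered. The document does not support that. It gives no r; above about 0.49 the interaction exceeds the stated power at 37 per arm, and if fewer than 25% are lost the threshold is lower. Losses above 25%, to which the complete-data rule and the exclusion of poorly fitted spectra could contribute, would raise it. Nor can a low r be inferred from Appendix section 5.1.2's remark that glutamate in these regions is hard to measure, because the same sentence reports good-quality signal in this population.

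The term ANCOVA could be meant as adjustment for baseline, in which case the power point falls away. But no covariate is named, and the effect said to be tested is the interaction.

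On mediation, a reader might infer that no mediation analysis will ever be done. A statistical analysis plan that is not shown could contain one. What remains is that the protocol's stated question goes further than the tests it sets out to answer it.

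**Conclusion.** The point holds for glutamate. The sizing and the test are on different scales, and at 37 per arm the stated 80% is met only if r is at least about 0.49. Over r from 0 to 0.8 the planned test's power runs from 52% to 99%, while baseline adjustment keeps at least 80% throughout. These figures rest on equal SDs at both visits and on 0.67 being a difference in units of the cross-sectional SD, which is how section 6.2 derives it. It is a dependence on an unstated quantity, not a demonstrated shortfall, and it does not carry over to fMRI or ASL.

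The mediation mismatch also holds, as one between the objective's wording and the tests written in the protocol. It needs no numerical assumption. Neither matter touches the trial's primary analysis.

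**What to change.** In Appendix section 7.2.3, replace the time-by-treatment interaction with a regression of day-28 glutamate on arm and the participant's own baseline glutamate. The sample size of 100 can then stand as justified in section 6.2, with no need to assume a value for r.

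For the objective, do one of two things. Either reword the Appendix synopsis and section 3.1 to ask about the effect of CBD on brain function and glutamate, which the planned tests can answer; or add one mediation model, labelled exploratory, linking day-28 glutamate to day-182 CAARMS severity, each adjusted for its baseline. The document gives no figure for the association between glutamate and CAARMS, so no power should be claimed for such a model without a stated assumption and range.

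The cost is wording only. Scans at baseline and day 28 and CAARMS at baseline and day 182 are already scheduled; no extra patients, visits or measurements are needed.
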